12.1 Sample Size Calculation

The primary parameter of this documentation is work productivity, which is captured by the number of missed working days. The sample size calculation is based on the results of an interim analysis of a documentation of adalimumab in RA with 4640 patients, of whom 1417 patients had been employed part time or full time. The mean number of missed working days was 26 days (standard deviation of 55 days) during the last 12 month prior to adalimumab therapy. The correlation between baseline and follow-up report is estimated with $r = 0.5$. According to these numbers, 850 employed patients are required to detect a mean difference of 5 days within 12 months at the 0.05 significance level (two-sided) with a power of 0.80. Since 30 % of patients are employed, a total number of about 2500 employed and non-employed patients are required in order to detect the specified difference in missed working days.

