8.2 Number of Patients to be Enrolled

The NIS will include about 2500 patients in order to provide for the final evaluation of missed working days a sample size of $n = 850$ employed patients who are temporarily on sick leave during the study (see also Section 12.1 “Sample Size Calculation”).

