Laboratory values: Hepatitis B, Hepatitis C, tuberculosis screening, TB prophylaxis (if necessary) ⁶	X	X ⁷	X ⁷	X ⁷				
Adverse events		X	X	X	X	X	X	X
Patient's compliance		X	X	X	X	X	X	X

¹ Month 60 or last visit

² after baseline visit (month 0) only if current radiograph is available or if indicated

³ after baseline visit (month 0) only for newly developed diseases or changed therapy

⁴ after baseline visit only for changes in therapy or dose

⁵ Data are part of the DAS28 (Disease Activity Score)

⁶ after baseline visit (month 0) only if data is available or if indicated

⁷ only TB prophylaxis documented

Table 2. Patient Schedule

	Month							
	0	3	6	12	24	36	48	60
Personal data	X							
Education	X							
Professional status	X		X	X	X	X	X	X
Missed working days (last 6 months)	X		X	X	X	X	X	X
Physician visits and hospitalization (last 6 months)	X		X	X	X	X	X	X
Days of impairment in non-occupational activities	X		X		X	X	X	X
Work ability (WPAI)	X	X	X	X	X	X	X	X
Exhaustion/fatigue (last 7 days)	X	X	X	X	X	X	X	X
Pain (last 7 days)	X	X	X	X	X	X	X	X
Functionality (HAQ)	X	X	X	X	X	X	X	X
Health-related quality of life (EQ-5D)	X	X	X	X	X	X	X	X
Patient's assessment of adalimumab ther- apy compared to previous therapies		X	X	X	X	X	X	X
Participation Abbott Care service program	X	X	X	X	X	X	X	X

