12.3 Missing Values

Missing observations will be documented as missing values. Instructions for the minimum documentation required for a patient to be evaluable will be established in the SAP.

All data will be analyzed on the basis of “observed cases”. For the statistical analysis of data concerning the course of disease, the health-related economic parameters and

the health-related quality of life (if related to changes from baseline values), an additional approach will be followed considering only patients with complete data at all visits.

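### Section 12.1 requires 850 employed patients, but 30% of 2500 is only 750, so the stated 80% power is not delivered; nor do the printed inputs lead to 850.

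*Combined protocol and SAP*

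**What the plan says.** Section 12.1 of the combined protocol and SAP makes missed working days the primary parameter and sizes the study on it. The source is an interim analysis of an earlier adalimumab documentation with 4640 patients, 1417 of them employed. It gives a mean of 26 missed days and a "standard deviation of 55 days) during the last 12 month prior to adalimumab therapy". Baseline and follow-up counts are taken to correlate at r = 0.5. From these inputs, at two-sided 0.05 and power 0.80, the section concludes that "850 employed patients are required to detect a mean difference of 5 days within 12 months". It then converts to total enrolment: "Since 30 % of patients are employed, a total number of about 2500 employed and non-employed patients are required".

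Section 8.2 repeats the link. About 2500 patients are to be included "in order to provide for the final evaluation of missed working days a sample size of" 850, described there as "employed patients who are temporarily on sick leave during the study".

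Four other places bear on the calculation:

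- Table 2 (Section 8.5.1) collects "Missed working days (last 6 months" at baseline and from Month 6 onwards.
- Section 8.4 ends a patient's documentation at five years or when adalimumab stops.
- Section 12.3 states: "All data will be analyzed on the basis of" observed cases.
- Amendment I, Section 1.9, reports about 50% premature discontinuation over 60 months in adalimumab documentations and enlarges its own sample for it. Section 12.1 has no such allowance.

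**The concern.** The required number, the share employed and the total enrolment cannot all be right, because 2500 patients at 30% employed do not supply 850. Separately, a reader who applies the usual paired formula to the printed SD and correlation does not arrive at 850.

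This is the only calculation behind 2500. If it is wrong, the plan overstates its power for the parameter that sizes the study, and the smallest change it can detect with 80% power is larger than the 5 days stated. Three further gaps affect what the calculation means: there is no dropout allowance, the recall period differs from the period of the SD, and Sections 8.2 and 12.1 describe different populations.

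**Working it through.** **Inputs, all from Section 12.1:** SD 55 days (12 months before therapy), r = 0.5, difference 5 days, two-sided alpha 0.05, power 0.80, 30% employed (1417/4640 = 30.5%), total about 2500. The follow-up SD, written s2 below, is not printed.

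**Step 1: enrolment to employed patients (no assumption needed).**

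- 2500 × 0.30 = 750; 2500 × 1417/4640 = 763.
- Shortfall against 850: 100 or 87.
- Enrolment needed for 850: 850/0.30 = 2833; 850/(1417/4640) = 2783.
- Share employed needed at 2500: 850/2500 = 34%.

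**Step 2: try to reproduce 850.** For a within-patient change in a single-arm cohort:

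- SD of change = √(55² + s2² − 2 × r × 55 × s2)
- n = (1.960 + 0.842)² × (SD of change)² / 5²

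| s2 | r | SD of change | n |
|---|---|---|---|
| 55 (equal SDs, assumed) | 0.5 | 55.0 | 950 (952 by paired t-test) |
| 55 | 0.5525 | 52.0 | 850 |
| 48.4 | 0.5 | 52.0 | 849 (852 by paired t-test) |
| 44.4 (= 55 × 21/26, SD falling with the mean) | 0.5 | 50.5 | 802 (805 by paired t-test) |

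With equal SDs the printed inputs give about 950. To get 850, one needs an input the plan does not print, such as r of about 0.55 or a follow-up SD of about 48.4. Other standard variants also miss: a one-sided test gives 749, the residual SD 55 × √(1 − 0.5²) gives 713, and two independent groups give 1900 per group.

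**Step 3: power at the number the plan will actually have, before dropout** (noncentral t, two-sided 0.05, difference 5 days).

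| SD of change | Power at 750 / 763 | Detectable difference at 80% power, days |
|---|---|---|
| 55.0 (equal SDs) | 70.1% / 70.8% | 5.63 / 5.59 |
| 52.0 (the value that makes 850 correct) | 74.8% / 75.5% | 5.33 / 5.28 |
| 50.5 (SD falls with the mean) | 77.2% / 77.9% | 5.18 / 5.13 |

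For 80% power at 750 to 763, the SD of change would have to be about 49 days. That means r of about 0.60 with equal SDs, or a follow-up SD of about 38 to 40 at r = 0.5. In that case 850 would not be the requirement. With SD 55, even 850 patients would give only 75.4%.

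**Step 4: dropout.** Neither document gives a 12-month retention figure. As an illustration only, applying the 50% from Amendment I to Month 60 leaves 375 to 382 patients and power of 42-43%. This assumes that SD 55 and r = 0.5 carry over to Month 60 and that everyone remaining is still employed.

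**Step 5: period and population.** The SD and the 5-day target refer to 12 months, while Table 2 asks about 6. The Month 6 and Month 12 reports together cover the first treatment year, but the baseline report covers only half of the year before. Section 12.1 sizes on all employed patients, whereas Section 8.2 counts only those with sick leave during the study. If Section 8.2 is meant literally, the shortfall is larger still.

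**The case against.** Step 1 is hard to contest: the word about does not cover a gap of 283 to 333 patients. The stronger objections concern the rest.

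- **850 is undetermined, not disproved.** The follow-up SD is unprinted, and 48.4 would be unremarkable if missed days fall on treatment. Rounding could do it too: SD 54.5 with r = 0.544 gives 54.5 × √(2 × 0.456) = 52.0 and n = 850, though both values lie near their rounding limits. This stands. The 950 depends on the equal-SD assumption, and what can be said firmly is that the printed inputs do not lead to 850.
- **On the plan's own terms the loss is about 5 points of power** (80% to about 75%), and 70-71% rests on an SD the plan does not state. This is fair, and both figures are given with their conditions.
- **A smaller residual variance would rescue 750.** It would (n = 713 with the residual SD), but then 850 is wrong. Every route leaves a printed figure to correct.
- **The Month 60 figure may be beside the point.** The target is a 12-month difference, and the final evaluation may mean the analysis after follow-up closes and not Month 60 values. This is a reasonable reading. The lasting point is that no powered visit is named and no dropout is allowed for.
- **Little depends on it.** Section 12.4 calls the analyses exploratory and Section 12.5 makes them mainly descriptive. This is true, and it limits the seriousness but does not make the figures right.

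**Conclusion.** The concern holds. That 2500 patients at 30% employed yield 750 to 763 and not 850 is a contradiction within Section 12.1, carried into Section 8.2, and it rests on no assumption. If 850 is the number for 80% power, the plan delivers about 75% and can detect 5.3 days. If the follow-up SD equals the baseline SD of 55, the requirement is about 950, and the plan delivers 70-71% and can detect 5.6 days. If the SD falls in proportion to the mean, power is 77-78%. All these figures are before dropout.

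The missing dropout allowance, the 6-month recall against a 12-month SD, and the sick-leave wording in Section 8.2 are secondary mismatches that the same edit should resolve. This should be fixed, but it is a correction of stated figures in an exploratory study and threatens no decision rule.

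**What to change.** In Section 12.1:

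- Print the formula and the follow-up SD or the SD of change. Then either keep 850 with the inputs that give it, or restate the requirement as about 950 if the SDs are taken as equal.
- State that about 2500 enrolled yields about 750 to 763 employed patients, with the power and detectable difference that follow from the printed inputs: 70-71% and 5.6 days with SD 55 at both times, or about 75% and 5.3 days if the inputs support 850. Say that this is before dropout.
- Name the time point that is powered. If it is Month 60, add the expected retention.
- Reconcile the 12-month SD and 5-day target with the 6-month recall in Table 2, chiefly at baseline.

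In Section 8.2, make the number and the population match Section 12.1, that is, all employed patients and not only those on sick leave.

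The cost is protocol and SAP wording. Enrolment and data collection do not change. The stated power becomes less favourable.

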12.2 Analysis Population(s)

The data of all documented patients will be used in the statistical analysis of tolerability and safety of adalimumab. The data of patients whose RA had been treated with adalimumab previously will be excluded from the analysis of efficacy.

12.3 Missing Values

Missing observations will be documented as missing values. Instructions for the minimum documentation required for a patient to be evaluable will be established in the SAP.

All data will be analyzed on the basis of “observed cases”. For the statistical analysis of data concerning the course of disease, the health-related economic parameters and

the health-related quality of life (if related to changes from baseline values), an additional approach will be followed considering only patients with complete data at all visits.

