### **1.9 Sample size estimation**

*Sample size estimation for AGIL-CV as a supplement to AGIL:*

The sample size estimation is based on published data concerning the blood pressure of RA patients (14):

Assuming an alpha and beta error of 5% each, the following minimum number of RA patients is required at the evaluation time points of Months 12, 24 and 60:

- N=128 patients are required in order to detect a mean systolic blood pressure difference of 10 mmHg (given a mean systolic blood pressure of 128 mmHg with a standard deviation of 18 mmHg).
- N=136 patients are required in order to detect a mean diastolic blood pressure difference of 5 mmHg (given a mean diastolic blood pressure of 74 mmHg with a standard deviation of 11 mmHg).

In documentations with adalimumab, premature discontinuation has been observed for approx. 50% of patients in the course of a 60-month documentation duration. If this rate is taken into account; an overall number of N=300 patients is sufficient to address the primary research questions given the above-named estimations.

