## 1.10 Biometrics concept of AGIL-CV

*Biometrics concept as an addition to AGIL-CV:*

Using stepwise regression analyses with forward and backward techniques, all partial correlations between the primary parameters and the other disease and patient characteristics are determined at baseline. The impact of disease and patient characteristics on the changes in each of the primary parameters is established by means of these regression analyses at Months 12, 24 and 60. In particular, the DAS28 response (defined as the critical difference [dcrit] of  $\leq -1.8$  points, constituting an improvement of 1.8 points in DAS28) or DAS28 nonresponse was used as a coded variable.

In addition, the observed difference between the DAS28 responders (patients with a dcrit of  $\leq -1.8$  at 5 of 7 visits) and the DAS28 nonresponders (dcrit  $> -1.8$ ) is tested using the general linear model. Missing data are replaced using the Last observation carried forward (LOCF) method.

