8.4 Study Duration

The duration of the whole NIS is estimated to be about 9 years.

Study start: March 2009

Recruiting phase: March 2009 – March 2012

Data completion: March 2017

Data analysis and final report: March 2017 – March 2018

For each individual patient, the NIS starts with the enrollment in the long term documentation at the beginning of the treatment with adalimumab and ends either after 5 years or with the termination of the adalimumab therapy.

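### Main AGIL plans no analysis covering all patients who start adalimumab, so Month 60 improvement describes mainly those still on drug and is likely overstated for starters by an unknown amount

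*Combined protocol and SAP*

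**What the plan says.** Section 12.3 of the AGIL documentation plan (the combined protocol and SAP) sets two approaches. The first is general: "All data will be analyzed on the basis of “observed cases". The second applies to changes from baseline in disease course, health-economic parameters and quality of life: "an additional approach will be followed considering only patients with complete data at all visits". The section contains no imputation, model-based or weighted analysis, and no rule for patients who stop. It defers only the minimum documentation for evaluability to a separate SAP.

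Section 8.4 says that each patient's participation "ends either after 5 years or with the termination of the adalimumab therapy". Section 7 places the final analysis of the primary objective, improvement from baseline, after 60 months of treatment.

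The main plan gives no discontinuation rate. The AGIL-CV amendment does, in its Section 1.9, for adalimumab documentations in general: "premature discontinuation has been observed for approx. 50% of patients in the course of a 60-month documentation duration".

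Two further passages matter. In Section 8.5.1 the physician schedule (Table 1) footnotes its last column "Month 60 or last visit", while the patient schedule (Table 2) carries no such note. Section 1.10 of the amendment has its own rule for AGIL-CV: "Missing data are replaced using the Last observation carried forward (LOCF) method".

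**The concern.** The study has a single arm, so no comparator shares the attrition. If about half of the starters have left by Month 60, the observed-case mean at that visit comes from a group selected by persistence. The completer set requires the same persistence and, in addition, no gaps. At Month 60 every completer is also an observed case and neither set contains a later value for a patient who stopped. Agreement between the two would therefore say nothing about the effect of stopping.

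Section 6 presents the study as covering patients treated in routine care regardless of comorbidity, severity or age. Readers will naturally take a Month 60 improvement as what a patient starting adalimumab can expect. If patients stop mainly because the drug did not help or was not tolerated, that reading is too favourable, and nothing planned in main AGIL would show by how much.

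**Working it through.** **The sponsor's own use of the 50% figure.** Section 12.3 contains no number to reproduce. In AGIL-CV Section 1.9, 300 × (1 − 0.5) = 150, which exceeds the 128 and 136 patients said to be needed at each evaluation. So 50% is the sponsor's working figure for loss by Month 60, although the main plan does not use it.

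**Inputs**
- q = 0.50, the share stopped by Month 60 (AGIL-CV Section 1.9; applying it to main AGIL is an assumption).
- f = mean improvement of stoppers ÷ mean improvement of stayers. The documents give no value, so it is varied.
- N = 2500 (Sections 8.2 and 12.1).

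**Stayers against all starters**

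All-starter mean = (1 − q) × D_stay + q × D_stop = D_stay × [(1 − q) + q × f].

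Ratio of stayer mean to all-starter mean = 1 ÷ [(1 − q) + q × f].

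| f | (1 − q) + q × f at q = 0.5 | Ratio | All-starter value if stayers improve by 5 days |
|---|---|---|---|
| 0 | 0.500 | 2.00 | 2.50 |
| 0.25 | 0.625 | 1.60 | 3.125 |
| 0.5 | 0.750 | 1.33 | 3.75 |
| 0.75 | 0.875 | 1.14 | 4.375 |
| 1 | 1.000 | 1.00 | 5.00 |
| 1.25 | 1.125 | 0.89 | 5.625 |

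The 5 days is the difference used in Section 12.1 and serves only as an illustration.

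Sensitivity to q at f = 0.5: with q = 0.3 the ratio is 1 ÷ 0.85 = 1.18, and with q = 0.6 it is 1 ÷ 0.70 = 1.43. The overstatement is then 18% to 43%.

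**Size of the completer set**

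About 2500 × 0.5 = 1250 patients would still be documented at Month 60. Assume that each remaining patient has complete data at each follow-up visit with probability 0.90 to 0.95, independently across visits. Neither assumption is in the documents.

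- Variables collected at all seven follow-up visits: 0.5 × 0.90^7 = 0.239 to 0.5 × 0.95^7 = 0.349, about 600 to 870 of 2500.
- Missed working days, not collected at Month 3 and so with six follow-up visits: 0.5 × 0.90^6 = 0.27 to 0.5 × 0.95^6 = 0.37 of those to whom the variable applies.

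The base of 2500 is generous. Section 12.2 removes patients previously treated with adalimumab from the efficacy analysis, and missed working days concern only the roughly 30% who are employed.

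**The two sets side by side**

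| | Observed cases | Completers |
|---|---|---|
| Month 60 | Documented at Month 60; last visits of stoppers may or may not be added | Subset of the former |
| Months 3 to 24 | Include patients who stop later | Exclude them |

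The two sets can therefore reveal selection at the early visits but not at Month 60.

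**The case against.** The strongest counter-argument is that an on-treatment description is a legitimate target. Section 6 speaks of change under long-term treatment, Section 7 says the aim is to explore, Section 12.4 calls the analyses exploratory, and Section 12.5 calls them principally descriptive. This stands, provided the tables say whom they describe. Section 12.3 does not require that.

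Four stronger readings are tempting, and the documents do not support them.

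- A reader might infer that the overstatement is proven. The documents give neither reasons for stopping nor outcomes afterwards. It is the plausible direction, but the table above includes zero and reversed bias.
- A reader might infer that no stopper can enter the Month 60 results. The physician-schedule footnote leaves open whether a stopper's last joint counts, CRP or ESR and DAS28 are analysed as Month 60. The footnote is absent from the patient schedule, which carries missed working days, WPAI, HAQ and EQ-5D, so it does not settle the matter for those variables.
- A reader might infer that attrition makes improvement appear to grow over time in both analyses. It can do so in observed cases, where the composition changes. It cannot in a fixed completer cohort, which is why that analysis is worth keeping.
- A reader might infer that a 40% success rate is really 20%. That halving follows from defining every stopper as a failure, and main AGIL defines no responder threshold. The 1.8-point DAS28 rule belongs to AGIL-CV.

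It can also be said that Section 12 leaves detail to a separate SAP that is not among these documents. That is true, and it may already deal with this. But Section 12.3 has already chosen the two approaches and does not signal a third.

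**Conclusion.** The point holds for main AGIL in limited form. As written, the plan yields no Month 60 estimate for all patients who start adalimumab, and its second analysis cannot reveal the effect of that gap at Month 60. Improvement is likely overstated if read as applying to starters. At 50% discontinuation the stayer figure ranges from 2.0 times the all-starter figure (f = 0) to equal (f = 1), and it understates if stoppers improve more. If stoppers end up worse than at baseline, the ratio exceeds 2.0.

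This rests on the amendment's 50% carrying over to the main cohort and on values of f that the documents do not supply. It does not extend to AGIL-CV, where LOCF is planned. It is a cheap improvement and does not invalidate the planned descriptive analyses.

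**What to change.** Amend Section 12.3, or settle it in the separate SAP before the database is opened for the first interim analysis:

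(a) Keep observed cases, labelled 'patients still on adalimumab at Month x', and show the number of starters and of discontinuations beside each visit's n.

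(b) State whether data recorded under "Month 60 or last visit" for patients who stopped are analysed as Month 60, and apply one rule to physician and patient variables.

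(c) Keep the completer analysis as descriptive only. Add, as the supporting analysis, a repeated-measures model using all observed visits of all efficacy patients. Choose a form suited to missed working days, which are strongly right-skewed (mean 26, SD 55 in Section 12.1, so the SD is about 2.1 times the mean of a non-negative count). State that the model assumes dropout is explained by observed data and that it estimates outcome under continued documentation on drug. That is not the outcome of all starters with stopping counted against the drug.

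(d) For that second quantity, add a conservative all-starters bound, such as no improvement from baseline after stopping. For any percentage reported as success or remission, put all starters in the denominator and count stopping as no success. The mean version is a bound only if stoppers do not fall below baseline on average, and the text should say so.

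Cost: SAP wording, one extra model per outcome and some table columns, with no new data collection. The downside is less favourable headline figures.
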